Duration of Syphilis RPR confirmatory testingImage: Confirmatory testingDuration of CT/NG GeneXpert testingImage: Confirmatory testingDuration of TV OSOM testingImage: Confirmatory testingDuration of pregnancy testingImage: Confirmatory testingDuration of UTI dipstick testingImage: Confirmatory testingDuration of UTI dipstick testingImage: Confirmatory testingTotal duration spent at RU clinic with nurseImage: Confirmatory testingTotal duration spent at RU clinic with physicianImage: Confirmatory testingTotal duration spent at RUImage: Confirmatory testing	Duration of Syphilis Determine rapid testing		
Duration of CT/NG GeneXpert testing Image: Comparison of CT/NG GeneXpert testing Duration of TV OSOM testing Image: Comparison of CT/NG GeneXpert testing Duration of pregnancy testing Image: Comparison of CT/NG GeneXpert testing Duration of pregnancy testing Image: Comparison of CT/NG GeneXpert testing Duration of UTI dipstick testing Image: Comparison of CT/NG GeneXpert testing Total duration spent at RU clinic with nurse Image: Comparison of CT/NG GeneXpert testing Total duration spent at RU clinic with physician Image: Comparison of CT/NG GeneXpert testing Total duration spent at RU Image: Comparison of CT/NG GeneXpert testing Total duration spent at RU Image: Comparison of CT/NG GeneXpert testing Total duration spent at RU Image: Comparison of CT/NG GeneXpert testing	Duration of Syphilis RPR confirmatory testing		
Duration of TV OSOM testing Image: Constraint of the second s	Duration of CT/NG GeneXpert testing		
Duration of pregnancy testing Image: Constraint of UTI dipstick testing Duration of UTI dipstick testing Image: Constraint of UTI dipstick testing Image: Constraint of UTI dipstick testing Image: Constraint of UTI dipstick testing Image: Constraint of UTI dipstick testing Image: Constraint of UTI dipstick testing Image: Constraint of UTI dipstick testing Image: Constraint of UTI dipstick testing Image: Constraint of Constraint of UTI dipstic with physician Image: Constraint of Constraint of UTI dipstic testing Image: Constraint of Constraint of UTI dipstic testing Image: Constraint of UTI dipstic testing Image: Constraint of UTI dipstic testing Image: Constraint of UTI dipstic testing Image: Constraint of UTI dipstic testing Image: Constraint of UTI dipstic testing Image: Constraint of UTI dipstic testing Image: Constraint of UTI dipstic testing Image: Constraint of UTI dipstic testing Image: Constraint of UTI dipstic testing Image: Constraint of UTI dipstic testing Image: Constraint of UTI dipstic testing Image: Constraint of UTI dipstic testing Image: Constraint of UTI dipstic testing Image: Constraint of UTI dipstic testing Image: Constraint of UTI dipstic testing Image: Constraint of UTI dipstic testing Image: Constraint of UTI dipstices Image: Constraint	Duration of TV OSOM testing		
Duration of UTI dipstick testing N Time in median minutes [IQR] Total duration spent at RU clinic with nurse	Duration of pregnancy testing		
NTime in median minutes [IQR]Total duration spent at RU clinic with nurseTotal duration spent at RU clinic with physicianTotal duration for laboratory testingTotal duration spent at RU	Duration of UTI dipstick testing		
Total duration spent at RU clinic with nurseImage: Constraint of the systemTotal duration spent at RU clinic with physicianImage: Constraint of the systemTotal duration for laboratory testingImage: Constraint of the systemTotal duration spent at RUImage: Constraint of the system		N	Time in median minutes [IQR]
Total duration spent at RU clinic with physician Image: Clinic with physician Total duration for laboratory testing Image: Clinic with physician Total duration spent at RU Image: Clinic with physician	Total duration spent at RU clinic with nurse		
Total duration for laboratory testing Total duration spent at RU	Total duration spent at RU clinic with physician		
Total duration spent at RU	Total duration for laboratory testing		
	Total duration spent at RU		

Total duration spent at RU clinic if CT/NG risk-score negative or chose not to	
wait for CT/NG results	
Total duration spent at RU clinic if CT/NG risk-score positive and chose to	
wait for CT/NG results	
Total duration spent at RU (with time for informed consent procedures and	
client satisfaction survey being substracted) ¹	
Total duration spent at RU (with time for informed consent procedures and	
client satisfaction survey being substracted) ¹ if CT/NG risk-score negative or	
chose not to wait for CT/NG results	
Total duration spent at RU (with time for informed consent procedures and	
client satisfaction survey being substracted) ¹ if CT/NG risk-score positive	
and chose to wait for CT/NG results	

Abbreviations: CT = *Chlamydia trachomatis*; IQR = inter-quartile range; NA = not applicable; NG = *Neisseria gonorrhoeae*; RU = Rinda Ubuzima; TV = *Trichomonas vaginalis*; UTI = urinary tract infection.

1. These procedures are study-specific and would not be performed in real clinic situations.

The overall costs will also be used for cost-effectiveness comparisons of syndromic management versus WISH procedures; this will be done to compare total numbers of participants that can be seen under syndromic management per time period versus total numbers of participants that can be seen under clinics that would follow WISH study procedures (while substracting study-specific components such as informed consent). These will be reported separately.

7.5 Procedure observations and clinic flow problems observed

During two monitoring visits performed by the UoL Project Manager, multiple participants were followed to observe whether procedures were performed correctly and what possible issues arose. Some remarks or issues during these observations were:

- The informed consent procedures, writing down of personal contact details, and the face-to-face interviews all took a long time. Anecdotal information given by participants indicates that this is no different from local health clinics, where long waiting times are also common.
- The informed consent procedures were well done.
- Some questions seemed to be difficult to understand for participants; especially questions related to time frame (e.g. "how many sex partners have you had in the last 12 months") had to be explained several times until the participant understood.
- The counselling procedures were well done; the participants seemed to appreciate that they could choose counselling topics themselves.
- Pelvic, bimanual and physical examinations were performed adequately.
- Sample collection was performed correctly and in accordance with the SOPs.
- The laboratory procedures were performed meticulously and correctly. No problems were observed during the usage of the GeneXpert platform. The number of invalid GeneXpert tests corresponded with those estimated by the manufacturer (< 5% of total).
- The diagnoses and treatment provided were in accordance to the POCT results, and in accordance to the SOPs.
- Partner notification was difficult as women often opted out for notification of their male partners. According to the RU physicians, many state not knowing who and/or where their partners are; others state that their partners went abroad.

In general, it was observed that the clinic flow was - albeit sometimes slow - performed well and that there were no major bottlenecks.

7.6 Client satisfaction survey

A Client Satisfaction Survey (CSS) was held among a random sample of the participants. 107 surveys were

conducted. They were conducted in a private space and by a clinician who had not interviewed them before and did not perform the normal WISH procedures, to ensure a lower social desirability bias.

	n (%) N = 107
Agreed with the following statements:	
- "The study staff were friendly"	
- "The instructions I received along the way were clear"	
- "The medical services I received were of good quality"	
- "The medical services I received were useful"	
- "The counselling/information I received was of good quality"	
- "The counselling/information I received was useful"	
Found (venous) blood sampling: - Very comfortable	
- Somewhat comfortable	
- Not comfortable at all	
- Not done	
Found fingerstick sampling: - Very comfortable	
- Somewhat comfortable	
- Not comfortable at all	
- Not done	
Found urine sampling: - Very comfortable	
- Somewhat comfortable	
- Not comfortable at all	
- Not done	
Found self-sampling of vaginal swabs: - Very comfortable	
- Somewhat comfortable	
- Not comfortable at all	
- Not done	
Found clinician-sampling of vaginal swaps: - very comfortable	
- Somewhat comfortable	
- Not como table at all	
Found the speculum and himanual examination: - Very comfortable	
- Somewhat comfortable	
- Not comfortable at all	
- Not done	
Found the face-to-face interviewing: - Very comfortable	
- Somewhat comfortable	
- Not comfortable at all	
- Not done	
Found the general counselling: - Very comfortable	
- Somewhat comfortable	
- Not comfortable at all	
- Not done	
- Missing	
Found the post HIV-test counselling: - Very comfortable	
- Somewhat comfortable	
- Not comfortable at all	
- Not done	
Estimated time participant spent at the clinic: median minutes [IQR]	

Abbreviations: CT = *Chlamydia trachomatis*; IQR = interquartile range; NA = not applicable; NG = *Neisseria gonorrhoeae*; STIs = sexually transmitted infections.

1. Multiple answers possible; totals may be more than 100%.

7.7 Staff survey

A staff survey was held with all the RU personnel directly involved in the WISH study, to inquire about their opinions of the services procedures offered during the WISH study, and whether there were improvements to make. The interviews were held by an external consultant who was not part of the RU team nor worked

at the Sponsor institution (UoL), to minimize social desirability bias. The survey was semi-structured; the consultant was allowed to inquire more in-depth after the initial answer was given.

Role at RU during WISH study: - Study physician - Research nurse - Laboratory technician - Outreach manager/data manager/receptionist In opinion of interviewee, type of women that were recruited into the WISH study after actively stopping targeting say workers ¹ :
- Research nurse - Laboratory technician - Outreach manager/data manager/receptionist In opinion of interviewee, type of women that were recruited into the WISH study after actively stopping taggeting say workers ¹ :
- Laboratory technician - Outreach manager/data manager/receptionist In opinion of interviewee, type of women that were recruited into the WISH study after actively stopping targeting say workers ¹ :
Outreach manager/data manager/receptionist In opinion of interviewee, type of women that were recruited into the WISH study after actively stopping targeting say workers ¹ :
In opinion of interviewee, type of women that were recruited into the WISH study after
actively stopping targeting say workers ¹ :
actively stopping targeting sex workers.
[categories to be made as needed]
Whether women that were seen during the WISH study were hard to find (according
to opinion of interviewee) ¹ :
[categories to be made as needed]
If recruitment could start again, issues that could have been improved according to
interviewee ¹ :
[categories to be made as needed]
n (%)
N=8
If the Ministry of Health in Rwanda decided to provide rapid STI testing on a larger
scale, places where interviewee would make the service available, and reasons ¹ :
[categories to be made as needed]
Estimated time that participant spent at RU for a Main Visit: shortest time in median
minutes [IQR]
Estimated time that participant spent at RU for a Main Visit: average time in median
minutes [IQR]
Estimated time that participant spent at RU for a Main Visit: longest time in median
minutes [IQR]
ractors mentioned that were important in determining the duration of a participant's
Sludy VISIL :
[Categories to be made as needed]
duration of Main Visit or other things related to WISH study:
[categories to be made as needed]
[categories to be made as needed]
[categories to be made as needed]
Time limit after which women started complaining ¹ :
[categories to be made as needed]
- NA: no or almost no contact with participants
Reasons why women did not complain:
[categories to be made as needed]
- NA: no or almost no contact with participants
Most nonular counselling tonics during counselling sessions ¹
[categories to be made as needed]
Least popular counselling topics during counselling sessions ¹ :
[categories to be made as needed]
- NA
Advantages of letting women choose their own counselling topics:
[categories to be made as needed]

- NA	
Disadvantages of letting women choose their own counselling topics ¹ :	
[categories to be made as needed]	
- NA / not answered	
Advantagesof risk scoring for CT/NG and syphilis ¹ :	
[categories to be made as needed]	
- NA	
Disadvantages of risk scoring for CT/NG and syphilis:	
[categories to be made as needed]	
- NA	
	n (%) N = 8
Examples of negative experiences with risk scoring:	
[categories to be made as needed]	
- No negative experiences	
- NA	
Estimated number of women who opted out for a certain service and reasons:	
[categories to be made as needed]	
- NA	
Most popular choice for participants when it comes to receiving CT/NG results (in	
case of positive risk score):	
- To wait at least 90 minutes for test result	
- To schedule additional visit at RU to obtain test result)	
- To receive a text message (and only follow-up in case of positive result)	
- To receive a call (and only follow-up in case of positive result)	
- 50% waited, 50% chose for a call back	
- NA	
Estimated number of women who underwent a pelvic examination (as a proportion of	
total study participants): - No women	
- Few women	
- Less than half of the women	
- More than hall of the women	
Estimation that this number of pelvic examinations conducted appropriate, too many,	
or too few:	
[categories to be made as needed]	
- NA	
Choice between self-sampling and clinician-sampling for vaginal testing: how many	
women opted out for clinician-sampling, and reasons why ¹ :	
[categories to be made as needed]	
- NA	
Feedback about clinical procedures during the WISH study:	
[categories to be made as needed]	
- NA	
Feedback about laboratory procedures during the WISH study ¹ :	
[categories to be made as needed]	
- NA	
What the study physician would choose between syndromic management, risk	N = 2

scoring followed by POC testing, or POC testing for all women in clinic:	
[categories to be made as needed]	
Aspects of POC testing that study physician considered difficult to do / interpret or	N = 2
difficult to communicate with patient:	
[categories to be made as needed]	
Whether physician trusted POC test results:	N = 2
[categories to be made as needed]	
Advantages and disadvantages of communicating with women via text message ¹ :	
[categories to be made as needed]	
Whether interviewee heard of any breaches of confidentiality:	
[cases to be described as needed]	
- None reported	
	n (%)
	N = 8
Estimated ratio of sexual partners reached by partner notification: - No partners	
- A few partners	
- Less than half of the partners	
- More than half of the partners	
- Most of the partners	
- All of the partners	
- NA / doesn't know	
Most popular methods of partner notification:	
 [categories to be made as needed] 	
- NA	
Ideal partner notification program ¹ :	
[categories to be made as needed]	
- NA	
Procedures of WISH study that could be improved ¹ :	
[categories to be made as needed]	
Any other comment by interviewee ¹ :	
[categories to be made as needed]	

Abbreviations: CT = *Chlamydia trachomatis*; FSW = female sex worker; IQR = interquartile range; NA = not applicable; NG = *Neisseria gonorrhoeae*; RU = Rinda Ubuzima; STIs = sexually transmitted infections.

1. Multiple answers possible; totals may be more than 100%.

7.8 Electronic participant identification register data

During the WISH study, participants could choose what forms of contact attempts they wanted in the case they had to be contacted for test results, treatment to be taken, missing information, to encourage partner treatment, and others. Unlike previous studies conducted at RU, we also added text messages to their mobile number in this.

	n (%)
	N = 705
Contact permissions given by participant ¹ :	
- Text message to own mobile phone	
- Phone call to own mobile phone	
- Phone call to emergency contact	
- Phone call to other mobile number	
- Email to participant	
- Letter to own address	
- Home visit to own address	
Preferred method of follow-up:	

- Text message to own mobile phone	
- Phone call to own mobile phone	
- Phone call to emergency contact	
- Phone call to other mobile number	
- Email to participant	
- Letter to own address	
- Home visit to own address	
- Missing	
Number of contact attempts during entire WISH study follow-up, per reason ¹ :	
- Outcome after treatment	
- To ask to come to RU to receive treatment	
- To ask to come to RU to receive results	
 To ask to come to RU for a lacking pelvic & bimanual exam 	
 To collect missing information on the source document / to correct data 	
 To communicate about problems with consent forms 	
 To ask about or encourage partner treatment 	
- As a reminder to come for an Additional Visit	
- To communicate results	
- To provide an explanation about medication	
 To answer questions about symptoms the participant has 	
	n (%)
	N = 705
Reasons for making an appointment for an additional visit in the ePIR ¹ :	
- To receive treatment	
- To receive laboratory results	
- To perform a pelvic & bimanual exam that could not be performed at Main Visit	
 To come together with partner for partner notification and treatment 	
- NA: no appointment made for additional visit	

Abbreviations: ePIR = electronic participant identification register; NA = not applicable.

1. Multiple answers possible; totals may be more than 100%.

7.9 Potential alternative risk score for Chlamydia and Gonorrhea

The performance of the CT/NG risk score is one of the secondary objectives of the WISH study (see section 1.1). Momentarily, the GeneXpert CT/NG assay is quite expensive; moreover, it is useful to use risk-scoring to avoid false-positive testing, especially in populations with low CT/NG prevalence. Therefore, a well-functioning CT/NG risk score is important.

Depending on the sensitivity and specificity of the CT/NG risk score, an alternative risk score will be devised. If performed, this alternative risk score is only intended as a tertiary analysis. Its SAP will be presented in a separate document. To make an alternative risk score, the best performing risk factors for CT/NG will be identified, and will be used individually and together; ROC curves will be made for these risk factors, both individually and put together, to find the risk score that provides the best sensitivity and specificity compared to gold standard testing of CT/NG (i.e., CT/NG GeneXpert test on everyone).

8. Appendices

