- The Rwandan VDS algorithms incorporate a predetermined set of questions for CT/NG risk scoring, as well as CT/NG treatment when a woman's partner has urethritis complaints. The WHO guidelines do provide the possibility for risk scoring but state that risk scoring should be guided by local epidemiology. *In this SAP, when evaluating the performance of the Rwandan guidelines, we will follow the Rwandan risk scoring as outlined in the algorithm.* One of the possible risk factors in the Rwandan guidelines is "2 or more sexual partners" but no time frame is given; we will use 2 or more sexual partners in the past 12 months. When evaluating the performance of the WHO guidelines, we will assume high risk for CT/NG based on the local epidemics in our research communities.
- In the Rwandan VDS algorithms, candidiasis is diagnosed based on the presence of unusual vaginal discharge and a low CT/NG risk score, while in the WHO guidelines candidiasis is only treated in the presence of typical signs and symptoms (vulval oedema/curd-like discharge, vulval erythema or excoriations). *In this SAP, we will follow each respective guideline when evaluating the performance of that guideline.*
- In the Rwandan algorithms, all female sex workers (FSWs) without symptoms are to receive presumptive treatment for NG, CT and TV. However, when they do report symptoms, the usual syndromic algorithms are to be used and no presumptive treatment should be given. No definition of FSW is given. In this SAP, we will define sex work by self-reported exchange of sex for money and/or goods in the past 12 months, and we will follow the Rwandan guidelines.

Flow diagrams of the WISH algorithms, as described in section 1.3, are shown in appendix 8.3.

2. Participant disposition

The number of participants was dictated by the available budget and no formal statistical power calculations were performed. 705 participants were enrolled in the study.

² World Health Organization, 2008: Report of the Expert Consultation and Review of the Latest Evidence to Update Guidelines for the Management of Sexually Transmitted Infections.

³ Republic of Rwanda – Ministry of Health, 2010: National Guide on the Care of Sexually Transmitted Infections – Manual of the Care Provider.

⁴ Republic of Rwanda – Ministry of Health, 2013: National Guidelines for Prevention and Management of HIV, STIS & Other Blood Borne Infections.

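### SAP 7.9 outlines a data-driven alternative CT/NG risk score without naming a validation step; unless corrected, its apparent performance would be optimistic beside the original score

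*SAP*

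**What the plan says.** SAP 7.9 makes the analysis depend on how the existing score performs: "Depending on the sensitivity and specificity of the CT/NG risk score, an alternative risk score will be devised". No threshold for that decision is given. The method follows: "the best performing risk factors for CT/NG will be identified, and will be used individually and together", with ROC curves "to find the risk score that provides the best sensitivity and specificity compared to gold standard testing of CT/NG". The reference is defined as "i.e., CT/NG GeneXpert test on everyone". The section does not list the candidate factors, say what makes a score best, or mention a split sample, cross-validation, bootstrap, optimism correction or second dataset.

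It also limits the status of the work: "If performed, this alternative risk score is only intended as a tertiary analysis", and "Its SAP will be presented in a separate document". That document is not among those available.

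Protocol 4.1 plans the original score from behavioural factors linked to these infections in the site's previous studies. SAP 4.1 gives its form in WISH: a fixed rule, positive if any one of four criteria is met, which decided who was offered CT/NG testing. SAP 5.3 and 5.4 report its performance against GeneXpert on all women.

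**The concern.** When factors, their combination and a cut-off are chosen because they do well in one sample, the performance measured in that sample is too high on average. Part of what was selected is chance. The outline in 7.9 is of this kind and stops before any step that would remove the excess.

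The original score was not tuned in these women. If both scores were shown against the same reference in the same sample, one figure would contain selection optimism and the other would not. The undefined trigger adds to this, because a chance poor result for the original score makes it more likely that an alternative is built.

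At stake is how well a future score would find infections. In the WISH algorithm the score decides who is offered testing, so overstated sensitivity means more missed infections than the report suggests.

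**Working it through.** **1. No plan figure to reproduce.** SAP section 2 says that "no formal statistical power calculations were performed", and 7.9 gives no target AUC, sensitivity or specificity.

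**2. Which women.** SAP section 2 states that "705 participants were enrolled in the study". Recruitment had ended by then. GeneXpert on everyone is the term that SAP 4.2, 5.3 and 5.4 use for WISH Main Visit samples, and 7.9 names no other data. The inference is therefore that development and evaluation use the same women. The number is at most 705, because SAP 4.2 drops missing and invalid results.

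**3. Prevalence range.** Protocol 4.3 expects 60 NG and 75 CT cases per 500 women: 60/500 = 12% and 75/500 = 15%. If independent, either infection has prevalence 1 − (1 − 0.12)(1 − 0.15) = 0.252. The simulation used 15% and 25%, or about 106 and 176 cases (705 × 0.15 = 105.75; 705 × 0.25 = 176.25). SAP section 2 reports a mid-study change in recruitment, so the actual prevalence may differ.

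**4. Simulation.** These inputs are assumptions, not in the documents:
- K = 10, 20 or 30 independent binary candidates, each present in 10–50% of women. SAP section 3 and the symptom table in 4.1 list over 50 items.
- Either no true predictors, or four with odds ratio 1.8.
- The 4 (K = 10) or 6 (K = 20, 30) candidates with the largest absolute value of sensitivity + specificity − 1 are kept, and a logistic score is fitted.
- The cut-off maximises Youden's J = sensitivity + specificity − 1.

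Optimism = performance in the 705 women used for selection − performance of the same score and cut-off in 40,000 new women, averaged over 300 simulated studies per scenario. Differences were taken before rounding.

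| Prevalence | K | True predictors | AUC same / new | AUC optimism | J same / new | J optimism |
|---|---|---|---|---|---|---|
| 15% | 10 | 4 | 0.660 / 0.629 | 0.031 | 0.252 / 0.182 | 0.071 |
| 15% | 20 | 4 | 0.671 / 0.604 | 0.067 | 0.276 / 0.146 | 0.130 |
| 15% | 30 | 4 | 0.675 / 0.598 | 0.076 | 0.278 / 0.136 | 0.142 |
| 25% | 10 | 4 | 0.661 / 0.647 | 0.014 | 0.250 / 0.212 | 0.038 |
| 25% | 20 | 4 | 0.666 / 0.630 | 0.037 | 0.264 / 0.183 | 0.081 |
| 25% | 30 | 4 | 0.658 / 0.600 | 0.057 | 0.250 / 0.140 | 0.110 |
| 15% | 10 | 0 | 0.581 / 0.500 | 0.081 | 0.139 / 0.000 | 0.139 |
| 15% | 20 | 0 | 0.612 / 0.500 | 0.112 | 0.190 / 0.000 | 0.189 |
| 15% | 30 | 0 | 0.625 / 0.500 | 0.124 | 0.208 / 0.001 | 0.208 |
| 25% | 10 | 0 | 0.567 / 0.500 | 0.068 | 0.114 / 0.000 | 0.114 |
| 25% | 20 | 0 | 0.592 / 0.500 | 0.092 | 0.156 / 0.000 | 0.156 |
| 25% | 30 | 0 | 0.605 / 0.500 | 0.104 | 0.173 / 0.000 | 0.173 |

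Optimism in J equals optimism in sensitivity + specificity. With true predictors, most of it falls on sensitivity. At 15% prevalence and K = 30, sensitivity was 62.9% in the selection sample against 50.7% in new women, and specificity 64.9% against 63.0%. At 25% and K = 10 the gap in sensitivity was only 62.7% − 59.7% = 3.0 points.

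**5. The original score.** Its four criteria and any-of-four cut-off were not chosen by performance in these data, so this source of optimism is absent from its estimate.

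**The case against.** The strongest reply is that the methods belong to a document nobody here has seen. Section 7.9 sketches how a score would be developed, not how its performance would be estimated or reported. A full bootstrap could sit in the separate SAP without contradicting a word of 7.9. The analysis may never be done, and it is tertiary if it is. This stands. A reader might infer that the plan commits the sponsor to reporting uncorrected figures, but silence in an outline does not show that.

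A reader might also infer a planned contest that the new score wins unfairly, or that a worse score would be recommended. No section specifies a head-to-head comparison or a recommendation, and the tables in SAP 5.3 and 5.4 have no row for an alternative score. The bias in a side-by-side reading is therefore conditional on someone making it.

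Nor should the original score's estimate be called unbiased in general. SAP section 2 says recruitment was changed because too many women scored positive, and that earlier participants, particularly those scoring negative, were asked to refer others. The documents also give no date on which the score was finalised. The supportable statement is narrower: it carries no optimism from selection by performance in these women.

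Finally, the size could be small, as the scenario with 10 candidates and 25% prevalence shows.

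What the reply does not remove is that the only procedure in the documents selects on performance, names no validation, and points to another SAP without promising one.

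**Conclusion.** The point holds in conditional form. Section 7.9 describes data-driven choice of factors and score, apparently in the same women (at most 705), with no internal or external validation named. If performance were reported from that process without correction, it would be optimistic on average, and placing it beside the original score would favour the alternative.

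The optimism is roughly 0.01 to 0.12 in AUC and 4 to 21 percentage points in sensitivity + specificity. With four modest true predictors the ranges are 0.014 to 0.076 and about 4 to 14 points. The upper ends come from the scenarios with no true predictors. All of this rests on the assumed number of candidates, true effects, prevalence and cut-off rule, so a narrower figure would claim more than the documents allow.

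No primary or secondary endpoint is touched: the secondary evaluation of the existing CT/NG score does not depend on this analysis. It is a cheap improvement to a tertiary analysis.

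**What to change.** State in 7.9, or state there that the separate SAP must specify, that:

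- the candidate list, the criterion for the best score and the trigger for building one are fixed before the analysis;
- the whole process (choice of factors, fitting, choice of cut-off) is repeated within each bootstrap resample, or within each fold of a cross-validation. With the bootstrap, corrected performance = apparent performance − the mean, over resamples, of (performance in the resample − performance of that resample's score in the full sample);
- optimism-corrected AUC, sensitivity and specificity are reported, and are the only figures for the alternative set beside those of the original score.

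Validation in a separate dataset would also serve, if one exists. The bootstrap or cross-validation needs no new data. The cost is a paragraph, modest extra computing, and less favourable reported figures for the alternative score.
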